4.2. Secondary Endpoints

The secondary endpoints are as follows:

- ED length of stay
- Hospitalization for pain control
- Return ED visits
- Hospitalizations, if not admitted to hospital on ED visits
- Re-hospitalizations, if admitted to hospital on ED visit and was discharged – we ignore those still hospitalized within 7 days of the index ED visits
- Day hospital visits, regardless admitted to hospital on ED visits or not
- A composite of return ED revisits or hospital re-admissions or day hospital visits (binary outcome with a cutoff at zero)

Methods of the final analyses: For the ED length of stay (from ED admission to discharge), a linear regression analysis similar to the primary outcome will be used to compare the length of stay between the two arms. For the hospital admission rate, chi-square test will be used to compare the admission rates between the two groups. For the count data (e.g., ED re-visits or hospitalizations or re-hospitalizations, or day hospital visits for VOE within 7 days after the recorded ED visit), it will be first evaluated by collapsing the data into a binary outcome with a cut off at zero and a chi-square test or Fisher exact test (if frequency is below 5 or less) to compare the re-admission rates or rate of a returned ED visit between the two groups. If there is sufficient spread in the count data, a Poisson regression approach will be used to test for protocol differences in the count outcome. (section 13.9.)

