8.2. Randomization and Patient Analgesic Protocols

After patients have provided informed written consent, they will be randomized to either

the weight-based analgesic protocol or a patient-specific analgesic protocol that will be developed by their hematologist/sickle cell team. A 1:1 treatment allocation will be used with site as the stratification variable. A computer-generated permuted block randomization schedule with stratification by clinical site will be prepared by the DCC senior statistician with block size randomly chosen that will not be revealed to investigators. This scheme provides chronological balance during enrollment with respect to the number of patients allocated to each treatment arm, and thus balances the treatment groups with respect to possible changes in the mix of patients over time. For the sites, the randomization will be available through the password protected and customized web-based electronic data capture (EDC) system. The EDC will be maintained by the DCC data management team. Treatment plans can be updated as needed by the hematologist.

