13. STATISTICAL CONSIDERATIONS

13.6. Overview

Detailed description of the plan for statistical analysis of each endpoint will be detailed in a Statistical Analysis Plan (SAP) that will be prepared after the final study protocol is approved. The SAP will be prepared by the DCC senior statistician under [name] supervision.

Descriptive statistics will be used to summarize patient socio-demographic and clinical characteristics. The analyses of primary and secondary outcomes as well as the summary description of pain-related side effects and safety will be carried out by the DCC statistical service. Means, standard deviations, medians, 25th and 75th percentiles, minimum and maximum will be presented for continuous variables; the number and frequency of patients in each category will be presented for nominal variables. For all analyses, a two-sided p-value ≤ 0.05 will be considered statistically significant. Analyses will be performed using SAS version 9.4 or higher software (SAS Institute, Inc., Cary, NC).

Multiple Comparisons: With the pre-specified primary and secondary analyses, we

recognize that there is a multiplicity of analyses to be performed, which leads to an increased probability that at least one of the comparisons could be "significant" by chance. There are adjustments (e.g., based on the Bonferroni inequality) that can be used to preserve the overall type I error level. To attempt to adjust for the effects of the repeated significance testing that will occur as part of potential interim monitoring (discussed below), plus to adjust for the multiplicity of secondary outcomes, would require that very small significance levels be used for every comparison. Rather than taking this approach we will be conservative in the interpretation of secondary analyses, taking into account the degree of significance, and looking for consistency across outcomes. The actual p-value for each comparison will be reported to aid in the overall interpretation. In addition to the pre-specified primary outcome, we will use pre-specified secondary outcomes and pre-specified subgroups to help avoid over-interpretation and to help guard against and reduce the problems inherent with multiple testing.

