Power calculation for the secondary outcomes are performed for the target sample size of 230 at 0.05 level. We do not expect any missing data in the secondary outcomes, as seen in the R34 study. For the length of ED stay from arrival to discharge, we have 83% power to detect a 30-minute difference in length of ED stay between the two analgesic protocols, assuming SD of 78. In the R34 study restricting to the first ED visit, the mean (SD) length time from arrival to discharge was 278 minutes (SD=78). For the secondary outcome of (yes/no) hospital admission in the 1st ED visit, returned ED visit or hospital admission within 7 days of the 1st ED visit, we use 15% as clinical significant difference. We have 64%, 78% and 94% power to detect a 15% difference in hospitalization rates in the 1st ED visit, in rates of returned ED visits within 7 days, and in rates of hospital admission within 7

days, respectively, with 0.05 type I error. We have assumed that hospitalization rates are 35% and 50%, the 7-day returned ED rates are 30% and 15%, and 7-day hospitalization rates are 20% and 5%, in the patient-specific and weight-based analgesic protocols, respectively. The assumptions on the hospitalization rates and the return ED visit rates are based on the observations in the R34 study.

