17. STUDY ENDPOINTS (TABLE)

17.1. Endpoints

	Treatment A N=	Treatment B N=	Estimate (95% CIs), SD	P-value
Change in Pain Score (Primary Endpoint)				
Length of Index ED Stay				
Hospitalization for Pain Control				
Return ED Visits				
Hospitalizations (if not admitted to hospital on Index ED visit)				
Re-hospitalizations (if admitted to hospital on Index ED visit, but discharged)				
Day Hospital Visits				
ED Revisits or Hospital Re-admissions or Day Hospital Visits Within 7 Days After the Index ED Visit (Binary Outcome with a Cutoff at Zero)				
Number of ED Revisits or Hospital Re-admissions or Day Hospital Visits After the Index ED visit				

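### Two 7-day hospitalization endpoints are tested in subsets defined by index admission, and the SAP has no clear, complete all-patient measure to show whether admissions were avoided or only deferred

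*SAP*

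**What the plan says.** Protocol 2.2 and section 11 list return ED visits, hospitalizations or day-hospital visits within seven days of the index visit, with no restriction by what happened at that visit.

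SAP 4.2 keeps index hospitalization for pain control as its own endpoint and divides later hospitalization in two. One part is "Hospitalizations, if not admitted to hospital on ED visits". The other is re-hospitalization among patients admitted and then discharged, with the rule that "we ignore those still hospitalized within 7 days of the index ED visits". Return ED visits, day-hospital visits and a composite of revisits, re-admissions and day-hospital visits are listed without that split. The methods paragraph applies chi-square or Fisher tests to these outcomes. The table in SAP 17.1 has a p-value column that covers both restricted rows, including "Hospitalizations (if not admitted to hospital on Index ED visit").

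SAP 7.7.2 adds a per-patient 7-day hospitalization category (0, 1, 2+) in which a patient who goes straight from the ED to the hospital has that stay counted as the first admission.

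Protocol 13.7 gives the planning rates, patient-specific arm first: "We have assumed that hospitalization rates are 35% and 50%, the 7-day returned ED rates are 30% and 15" (per cent), then 20% and 5% for 7-day hospitalization.

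**The concern.** Whether a patient is admitted from the index visit is decided after randomization and may depend on the assigned protocol. Patients not admitted in one arm are then a different selection from patients not admitted in the other, and a p-value comparing them does not test a randomized contrast. If one arm sends home patients whom the other would have admitted, its not-admitted group carries more risk, and the row can show harm even when the arm does better overall.

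The protocol's own planning rates pair fewer index admissions with more returns in the patient-specific arm. A reader of the final report will want to know whether admissions were avoided or only postponed. Separate rows for admission and for return give marginal rates, which do not settle that question.

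**Working it through.** **Inputs.** Two-sided 0.05 (Protocol 13.6); 230 patients for the secondary outcomes, with no missing data expected (Protocol 13.7); 1:1 allocation (Protocol 8.2), so 115 per arm. Rates below are patient-specific vs weight-based.

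**Step 1: reproduce the stated power.** Normal approximation with pooled null variance: power = Φ[(|p1 − p2| − 1.96·√(2p̄(1 − p̄)/n)) / √((p1(1 − p1) + p2(1 − p2))/n)], n = 115.

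| Outcome | Rates | Stated | Computed |
|---|---|---|---|
| Index admission | 35% vs 50% | 64% | 63.5% |
| 7-day ED return | 30% vs 15% | 78% | 78.1% |
| 7-day hospitalization | 20% vs 5% | 94% | 93.6% |

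The figures reproduce with every patient in the denominator. The hospitalization endpoint that was powered is therefore the unrestricted one.

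**Step 2: who is in the restricted rows.**
- Not admitted: 0.65 × 115 = 74.75 vs 0.50 × 115 = 57.5, about 75 vs 58.
- Admitted: 0.35 × 115 = 40.25 vs 57.5, about 40 vs 58. These are upper limits, because patients still in hospital are then removed.

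If all 7-day hospitalizations arose in patients not admitted (an assumption), the row would show 0.20/0.65 = 30.8% vs 0.05/0.50 = 10.0%. That is a 20.8-point difference where the same events differ by 15 points in all patients, with power of about 84%.

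**Step 3: selection in the not-admitted row.** The following is assumed, not taken from the documents. The patient-specific arm sends home 15% of patients who would otherwise be admitted; their later hospitalization risk is r; other patients sent home have 10% risk; admitted patients have no later event.
- Restricted row: (0.50 × 0.10 + 0.15r)/0.65. For r = 20%, 35%, 50% this is 12.3%, 15.8%, 19.2%, against 10.0%.
- Index admission or later hospitalization, all patients: 35 + 5 + 15r = 43%, 45.25%, 47.5%, against 50 + 5 = 55%.

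At r = 35% the restricted row shows an apparent harm of 5.8 points, while the all-patient measure shows a benefit of 9.75 points.

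**Step 4: what the separate rows leave open.** Index admission or 7-day ED return, from the planning rates. The documents do not give the overlap, so three cases are shown, each with the same pattern in both arms.

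| Overlap | Formula | Rates | Difference | Chance of p ≤ 0.05 |
|---|---|---|---|---|
| None | A + R | 65% vs 65% | 0 | 5% |
| Independent | 1 − (1 − A)(1 − R) | 54.5% vs 57.5% | −3 points | about 7% |
| Nested | max(A, R) | 35% vs 50% | −15 points | about 63% |

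With 7-day hospitalization in place of ED return, the rates are 55% vs 55%, 48% vs 52.5% and 35% vs 50%. One set of marginal rates thus fits no net effect or a 15-point benefit.

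**Step 5: the composite.** Take the no-overlap case, with ED return as the only return component. If the counting rule in SAP 7.7.2 applies to the composite's re-admission component, the composite is 65% vs 65%. If it does not, the composite is 30% vs 15%. The SAP does not say which.

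**The case against.** Four points can be made for the plan.

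- **A partial net measure exists.** A reader might infer that the SAP has no measure of net effect at all. SAP 7.7.2 does not support that: its 0/1/2+ category puts direct and later admissions on one scale for each patient. This stands as a limit on the point. But the category omits ED returns and day-hospital visits, has no row in SAP 17.1, has no test assigned by name, and conflicts with the split in SAP 4.2.
- **Nothing says inpatients are scored as event-free.** A reader might infer that time in hospital counts as freedom from return. The SAP drops patients still in hospital from the re-hospitalization row only. It is silent on how they are scored for ED return, day-hospital visits and the composite, and SAP 7.1 sets denominators only as non-missing values. The gap is an unstated rule.
- **Exact cancellation is one extreme.** The 65% vs 65% result needs zero overlap. A pure 15-point shift lifts ED return from 15% to 30% only if every moved patient returns (15 + 15r = 30 gives r = 1). The pilot study does not establish cancellation either: Protocol Table 3 gives marginal rates only. Admission plus ED return sums to 53.8% vs 54.3%, but admission plus 7-day hospitalization sums to 46.1% vs 50.3%. This stands, so the size must be given as a range.
- **Cautious reading is already promised.** Protocol 13.6 commits to conservative interpretation of secondary analyses and to looking for consistency across outcomes, and opposite movements would be visible side by side. That helps, but it neither restores a randomized comparison in the restricted rows nor supplies the patient-level overlap.

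**Conclusion.** The point holds for secondary endpoints. Two tested rows condition on a post-randomization outcome that the protocol assumes will differ by 15 points. They rest on about 75 vs 58 and at most about 40 vs 58 patients, while the stated 94% power belongs to an endpoint in all 115 per arm. SAP 4.2 and 7.7.2 disagree on how a direct admission counts, and the composite's meaning depends on which one governs.

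The net difference implied by the planning rates runs from 0 to 15 points in favour of the patient-specific arm across the three overlap cases. That range assumes the same overlap pattern in both arms. The documents do not support a claim that the net effect is zero, only that the separate rows cannot show what it is. The 35% and 50% admission rates are power assumptions, not predictions. The primary endpoint and its conclusion are unaffected.

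**What to change.** 1. Reconcile SAP 4.2, 7.7.2 and 17.1. State whether direct admission from the index ED visit counts in the composite, and how a patient still in hospital is scored for each 7-day outcome.
2. Analyse the 7-day objective in all modified-ITT patients with one pre-specified yes/no endpoint: index admission, or any return ED visit, hospitalization or day-hospital visit through day 7. Give it a row in SAP 17.1 and state how assignment to observation status is classified.
3. Report the two restricted rows descriptively, without p-values.

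The cost is SAP wording and one derived variable, since Protocol Appendix A already schedules the return components and index admission is already an endpoint. The plan gains one secondary endpoint and loses two p-values. The new endpoint gives an index admission the same weight as a day-hospital visit, so its components should still be shown beside it. Its power depends on the overlap: about 63% if nested and about 7% if independent at the planning rates. It should therefore be read mainly through its estimate and confidence interval.

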13.9. Analysis of Secondary Outcomes

Analysis of secondary outcomes will be carried out as follows. For the ED length of stay from ED arrival to discharge, a linear regression analysis similar to the primary outcome will be used to compare the length of stay between the two arms. For the hospital admission rate, chi-square test will be used to compare the admission rates between the two groups. For the count data (e.g., ED re-visits or hospitalizations for VOE within 7 days after the recorded ED visit), it will be first evaluated by collapsing the data into a binary outcome with a cut off at zero and a chi-square test or Fisher exact test (if frequency is below 5 or less) to compare the re-admission rates or rate of a returned ED visit between the two groups. If there is sufficient spread in the count data, a Poisson regression approach will be used to test for protocol differences in the count outcome.

13.10. Analysis of Exploratory Safety Outcomes:

The frequency with which various side effects, adverse event (AE) or serious adverse events (SAE) occur will be carefully tabulated and descriptively summarized. Statistical comparisons of the randomized arms with respect to these events will use chi-square, Fisher exact or other appropriate two-sample methods depending on the nature of the event, interpreting such comparisons in the context of differences between the two randomized arms in the primary and major secondary outcomes and bringing to bear clinical judgment as to the relative seriousness of these side effects and various adverse events.

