2.5. Randomization

After patients have provided informed written consent, they will be randomized to either the weight-based analgesic protocol or a patient-specific analgesic protocol that will be developed by their hematologist/sickle cell team. A 1:1 treatment allocation will be used with site as the stratification variable. A computer-generated permuted block randomization schedule with stratification by clinical site will be prepared by the DCC senior statistician with block size randomly chosen that will not be revealed to investigators. This scheme provides chronological balance during enrollment with respect to the number of patients allocated to each treatment arm, and thus balances the treatment groups with respect to possible changes in the mix of patients over time. For the sites, the randomization will be available through the password protected and customized web-based electronic data capture (EDC) system. The EDC will be maintained by the DCC data management team. Treatment plans can be updated as needed by the hematologist. (section 8)

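### The Poisson test of the 7-day counts makes no provision for variance differing from the mean, so its standard errors, intervals and p-values can be wrong in either direction

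*SAP*

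**What the plan says.** SAP 4.2 analyses the 7-day counts in two steps. First, "it will be first evaluated by collapsing the data into a binary outcome with a cut off at zero and a chi-square test or Fisher" comparison of the arms. Then: "If there is sufficient spread in the count data, a Poisson regression approach will be used to test for protocol differences in the count outcome". Protocol 13.9 gives the same second step: "If there is sufficient spread in the count data, a Poisson regression approach will be used". Neither document defines how much spread is sufficient, names a variance estimator for the Poisson model, or mentions overdispersion or another count model.

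SAP 4.2 lists the composite secondary endpoint as binary. A composite count also appears, in SAP 12.11 and in Tables 17.1 and 17.2. Table 17.1 labels it "Number of ED Revisits or Hospital Re-admissions or Day Hospital Visits After the Index ED visit" and gives it columns for an estimate with 95% CI and for a p-value. It does not say which test supplies that p-value.

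The significance rule is general (Protocol 13.6): "For all analyses, a two-sided p-value ≤ 0.05 will be considered statistically significant". The same section promises cautious interpretation of secondary results in place of a multiplicity adjustment.

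**The concern.** A Poisson model fixes the variance at the mean. If the true variance is larger, the model-based standard error is too small, the interval too narrow and the p-value too low. If it is smaller, the test is conservative and loses power.

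Both departures are plausible here. Some patients may return repeatedly, and an ED revisit and the admission it leads to may each be counted; either raises the variance. A count that rarely exceeds 1 tends the other way. At stake is whether a chance difference in 7-day use is reported as an effect of the dosing protocol, or a real one is missed.

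**Working it through.** **Inputs from the documents**
- 230 patients for the secondary outcomes (Protocol 13.7: "Power calculation for the secondary outcomes are performed for the target sample size of 230 at 0.05 level"), allocated 1:1, so 115 per arm; two-sided 0.05.
- R34 rates (Protocol 13.7, Table 3): return ED visit 15.7%, 7-day admission 9.8%, index admission 38.5%.
- Planning rates (Protocol 13.7): 7-day return ED 30% and 15% (mean 22.5%); 7-day hospitalization 20% and 5% (mean 12.5%).

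**The plan's own figures.** The only power figures for this family are for the binary outcomes: 64%, 78% and 94%. With the pooled two-proportion formula and 115 per arm I get 63.5%, 78.1% and 93.6%, so they reproduce. For return ED: null SE = √(2 × 0.225 × 0.775/115) = 0.0551; alternative SE = √((0.30 × 0.70 + 0.15 × 0.85)/115) = 0.0542; power = Φ((0.15 − 1.96 × 0.0551)/0.0542) ≈ 78%. No figure is given for the Poisson analysis.

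**Effect of dispersion.** Let φ = variance/mean. The false-positive rate of a nominal 5% Poisson Wald test is about 2[1 − Φ(1.96/√φ)].

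**Two-component count (assumption).** Each patient has at most one ED revisit and one admission, and a revisit ending in admission scores 2. The mean is 0.157 + 0.098 = 0.255.
- Independent events: variance = 0.157 × 0.843 + 0.098 × 0.902 = 0.221; φ = 0.87; error about 3.5%.
- Every admission through an ED revisit: E[X²] = 0.059 × 1 + 0.098 × 4 = 0.451; variance = 0.451 − 0.255² = 0.386; φ = 1.51; error about 11%.

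Simulation under the null (115 per arm, 40,000 trials), varying the overlap, which the documents do not give:

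| Admitted patients who also had an ED revisit | φ | Poisson error |
|---|---|---|
| 16% (independence) | 0.87 | 3.2% |
| 51% | 1.14 | 6.3% |
| 71% | 1.29 | 7.7% |
| 100% | 1.51 | 10.7% |

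With a robust variance the error stays between 4.5% and 5.0% throughout. φ passes 1 when P(both) = 0.157 × 0.098 + (0.255 − 0.221)/2 ≈ 0.0325, that is, when about one-third (0.0325/0.098) of admissions involve a revisit.

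At the averaged planning rates the mean is 0.35. Full overlap gives variance 0.10 + 4 × 0.125 − 0.35² = 0.4775, φ = 1.36 and error about 9.3%; break-even is at about one-half.

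**Recurrent events (assumption).** Negative binomial counts, 20,000 null trials, 115 per arm:
- P(any event) 15.7%: φ of 1.00, 1.19, 1.41 and 1.67 give Poisson errors of 4.8%, 6.5%, 9.2% and 12.5%.
- P(any event) 22.5%: φ of 1.00, 1.29, 1.66 and 2.15 give 4.7%, 7.9%, 12.2% and 17.6%.

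For φ from 1.19 to 2.15, sandwich errors give 5.0% to 5.9% and Pearson-scaled errors 4.6% to 5.1%.

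**What could lower φ.** SAP 7.7.2 counts a direct ED-to-hospital admission as the first admission and groups hospitalizations as 0, 1 or 2+. If index admissions entered the composite, independently of the rest, the full-overlap case would have mean 0.255 + 0.385 = 0.640, variance 0.386 + 0.385 × 0.615 = 0.623, φ = 0.97 and error about 4.7%. Limiting the count to 2 also pulls φ down: binomial counts with at most two events and mean 0.2 have φ = 0.90 and reject 3.6%.

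**The case against.** A reader might infer that the plan switches to Poisson exactly when Poisson is invalid, because the trigger is spread. The documents do not support that. The sentence follows the collapse to any/none, and its natural meaning is that enough values lie above 1 for a count model to add something. Spread is not overdispersion: simulated Poisson counts with mean 1.0 or 1.5, where 26% or 44% of patients have two or more events, reject at 5.1%. At this trial's low rates marked spread would often go with overdispersion, since a true Poisson count would put only about 1.3% to 2.8% of patients at two or more, but that is an inference.

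A reader might also infer that the composite count is overdispersed by construction. No section says a revisit ending in admission scores 2, and even under that scoring independent events give a ratio of 0.87. The 11% is the upper end for the two components, not an expected value.

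It is also fair to say that the text names no variance estimator, so model-based errors are inferred from silence; that the any/none test comes first and is untouched by dispersion; and that Protocol 13.6 commits to cautious reading of secondary results. These points limit the consequences. They do not remove the gap: cautious reading does not correct a standard error, and the count result has its own interval and p-value.

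**Conclusion.** The point holds as a minor one. The plan names Poisson regression as the test of the 7-day counts and does not protect its standard errors against variance unequal to the mean. The direction and size of the error are unknown because the documents give no dispersion. Under the two-component assumption with R34 rates the false-positive rate lies between about 3.5% and 11% at nominal 5%. Recurrent or day hospital visits could raise it; the negative binomial scenarios reach 17.6% at a ratio of 2.15. Including index admissions or capping at 2+ could lower it. The documents do not show that the intervals will be too narrow, only that they may be. The primary endpoint and the chi-square and Fisher tests are not affected.

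**What to change.** Add to SAP 4.2 that whenever the Poisson model is fitted, inference will use robust (sandwich) or Pearson-scaled standard errors, or negative binomial regression if the counts are overdispersed. Sandwich or scaled errors correct in both directions; the negative binomial addresses only overdispersion. Keep the any/none chi-square or Fisher test as the first analysis.

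The cost is a short SAP edit and a SAS option, with no new data or patients. Intervals become slightly wider when counts are overdispersed, and with 115 per arm the sandwich test can run a little above nominal (up to about 6% in the simulations). The sufficient-spread condition need not be dropped. Nor need a revisit with admission be redefined as one event: that would change the endpoint and require linking visits to admissions.
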